- 1) Inactivated influenza vaccine recipient controls who received the current IIV formulation (trivalent or quadrivalent) but not Q/LAIV for the season at a Kaiser health maintenance organization (HMO) during the same month that the reference Q/LAIV recipient was vaccinated will be identified and matched based on age (year) and medical center relative to concurrent reference Q/LAIV recipients, using frequency matching. For children 2 to 4 years of age, matching by age will be based on calendar quarter of birth rather than year. Factors such as gender and prior health care utilization level will be included as covariates in the proposed Cox proportional hazards model.
- 2) Unvaccinated controls who did not receive any influenza vaccine for the season will be identified and matched based on age (year) and medical center relative to concurrent reference Q/LAIV recipients using frequency matching. For children 2 to 4 years of age, matching by age will be based on calendar quarter of birth rather than year. Factors such as gender and prior health care utilization level will be included as covariates in the proposed Cox proportional hazards model. Unvaccinated controls will be followed from the date of vaccination of the reference Q/LAIV recipient (the index date).

Health care utilization levels will be defined as “high” ( $\geq 2$  visits to a Kaiser HMO within the 6 months prior to the date of vaccination of the reference Q/LAIV vaccinee) or “low” ( $\leq 1$  visit).

The study is expected to begin in the fall of 2013 following the launch of Q/LAIV and to be completed in a single influenza season. However, if fewer than 10,000 Q/LAIV recipients 2 through 8 years of age are identified following the 2013-2014 influenza season, the study will be continued for additional seasons until enrollment of 10,000 Q/LAIV recipients is completed. A detailed description of safety follow-up is described in Section 11. Data will be collected on subjects for 180 days following vaccination (or the index date for unvaccinated controls).

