**Table 9.3-1 Summary of Planned Analyses**

Event of Interest	Period at Risk After Vaccination	Reference Period
Hypersensitivity MAEs a Seizures/convulsions MAEs a	0-3 days c	7-9 days d
Lower respiratory MAEs Wheezing MAEs Guillain-Barré syndrome MAEs a Bell's palsy MAEs a Encephalitis MAEs a Neuritis MAEs a Vasculitis MAEs a Any hospitalization Respiratory hospitalization b	1-42 days c (1-14 days and 15-42 days)	43-84 days
Narcolepsy/cataplexy MAEs a	1-180 days c	NA

MAE = medically attended event; NA = not applicable

a Narratives of each case will be included in the final clinical study report.

b A respiratory hospitalization will be defined by the ICD-9-CM codes sets for lower respiratory MAEs and wheezing MAEs.

c It is not possible to detect from clinical databases whether an event occurring on the day of vaccination began prior to or after administration of vaccine, although events of hypersensitivity or seizures/convulsions may occur just subsequent to vaccination but are unlikely to be recorded on the same day prior to vaccination. As a result, the period at risk after vaccination for events of hypersensitivity and seizures/convulsions begins on the day of vaccination (Day 0), and the period at risk after vaccination for all other events of interest begins 1 day after vaccination (Day 1).

d The reference period for the period at risk for 0 to 3 days was defined from 7 to 9 days to take into account cyclical variations that may occur during the same days of the week.

An MAE is defined as a coded medical diagnosis made by a health care provider and associated with a medical encounter (ie, visit to a medical clinic or emergency department, or a hospital admission). One or more MAEs could be assigned for a single encounter.

For MAEs of Guillain-Barre syndrome, Bell's palsy, encephalitis, neuritis, vasculitis, and narcolepsy/cataplexy, events will only be counted if the subject does not have a prior record of the event in the 12 months prior to vaccination (or index date for unvaccinated controls).

In addition, listings of any hospitalization within 180 days, any deaths throughout the entire study period, and exposed pregnancies throughout the entire study period will be provided.

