#### **9.5 Study Size**

Since there are no identified safety concerns with Q/LAIV, this post-marketing safety assessment is hypothesis generating and will include multiple statistical comparisons.

Enrollment of at least 10,000 children 2 through 8 years of age is planned. A sample size of 10,000 children will provide approximately 90% power to observe a statistically significant increase in relative risk (RR) of 1.5 for an event that occurs in 1 in 100 subjects in the comparison group. The study will also be able to rule out with 95% probability the occurrence of an event at a rate of 0.03% (1 in 3,333 subjects) assuming that incidence of the event follows a Poisson distribution. Enrollment is expected to be completed in the 2013-2014 influenza season but the study will be continued for additional seasons, if needed, until enrollment of 10,000 Q/LAIV recipients 2 through 8 years of age is completed to fulfill the postmarketing commitment to the FDA.

However, because the study is expanded to adolescents and adults up to 49 years of age, it is expected that a total of approximately 80,000 individuals will be enrolled (including approximately 10,000 to 30,000 individuals in each of the following 4 age groups: 2 to 4 years, 5 to 8 years, 9 to 17 years, and 18 to 49 years of age) during the 2013-2014 influenza season. Enrollment of 20,000 children per age group will provide approximately 90% power to observe a statistically significant increase in relative risk (RR) of 1.5 for an event that occurs in 1 in 200 subjects in the comparison group. A sample size of 20,000 will also be able to rule out with 95% probability the occurrence of an event with an incidence rate of 0.015% (1 in 6,666 subjects).

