## 9.7.3 Planned Analyses

Tabular summaries will be presented by treatment group. Categorical data will be summarized by the number and percentage of subjects in each category. Continuous variables will be summarized by descriptive statistics, including mean, standard deviation, median, minimum, and maximum. The age, gender, medical center, and prior year health care utilization level of the Q/LAIV and control groups will be summarized for descriptive purposes. Race information is not available in the Kaiser HMO databases.

Rates of events will be presented per 1,000 person-years. All statistical tests will be 2-sided and performed at the significance level of 0.05. Due to the exploratory nature of the study and the lack of formal hypothesis testing, multiple CIs will be constructed in the primary analysis without multiplicity adjustment. Due to the large number of unadjusted CIs to be evaluated, it is expected by chance alone that a number of CIs will not include one and suggest higher or lower event rates in the Q/LAIV group. Therefore, further statistical and medical assessments may be performed for events with observed increases that are statistically significant and/or medically important.

Incidence rates of adverse events of interest during periods at risk after Q/LAIV vaccination will be compared to incidence rates during reference periods later in the follow-up as presented in [Table 9.3-1](#) (within-cohort analysis) and to incidence rates in controls (matched unvaccinated subjects and matched IIV recipients).

Incidence rates will be reported as subjects with an event per 1,000 person-years. If a subject has more than one event in the analysis window, the subject will be counted only once for the analysis. Relative risks (RR) and corresponding 95% CIs will be constructed for each event for safety comparisons with control groups. Crude RR and adjusted hazard ratio (HR) and corresponding 95% CIs for each event will be derived:

- Crude RR and exact 95% CI will be calculated without adjustment of any covariate.
- Adjusted HR and corresponding 95% CI will be obtained using Cox proportional hazards model with calendar time data input adjusting for seasonal changes in

background rates and other confounders. This multivariable analysis is detailed in Section 9.7.4.

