Statistical significance will be declared based on the multiple variable analysis using the Cox model. However, if the 95% CI of adjusted HR or p-value cannot be estimated, the exact method without adjustment of covariates will be used. A statistically significantly increased risk associated with Q/LAIV vaccination will be declared if the lower bound of the HR 95% CI is  $> 1.00$ . Likewise, a statistically significantly decreased risk associated with Q/LAIV vaccination will be declared if the upper bound of the HR 95% CI is  $< 1.00$ . Statistical significance will be evaluated before rounding. The corresponding p-values also will be provided. If any control group has zero events, the corresponding RR will not be estimable due to a zero value of the denominator. If the p-value is available, statistical significance will be declared according to the p-value at the 95% significance level.

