#### **9.7.4.1 Within-cohort Analyses**

Within-cohort analyses will be conducted among Q/LAIV recipients to see if the incidence of safety outcomes is higher within an immediate post-vaccination “risk” period (eg, 0 to 3, 1 to 14, 15 to 42, and 1 to 42 days post vaccination) compared to later “reference” periods, ie, 7 to 9 days post vaccination for the risk period of 0 to 3 days, 43 to 84 days post vaccination for the risk periods of 1 to 14, 15 to 42, and 1 to 42 days.

This will be accomplished in the Cox models by evaluating the main effect of “period,” defined as a time-dependent variable using the counting-process style of data input. Covariates, stratification factors, and the calendar time structure will be incorporated to control for the effects of age, gender, level of health care utilization, and seasonal difference in background event rates. The main effect variable of “period” will compare post-vaccination “risk” periods to “reference” periods occurring after the risk period.

For each study subject, the beginning of each reference period will follow the end of the risk period.

For example:

*riskperiod03*: 1 = risk (Days 0 through 3)

0 = reference (Days 7 through 9)

*riskperiod142*: 1 = risk (Days 1 through 42)

0 = reference (Days 43 through 84)

If specific results from the primary analyses identify a statistically significant increased risk associated with Q/LAIV administration, additional models with main effects structured to compare the “risk” periods to “reference” periods occurring prior to vaccination may be constructed. To reduce the potential bias associated with the “healthy patient effect,” the reference period prior to vaccination would exclude the week immediately prior to vaccination.

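### The within-cohort Days 1-14 versus Days 43-84 comparison has no guard against the healthy patient effect, so for acute respiratory outcomes its no-effect hazard ratio can lie below 1

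*Protocol*

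**What the plan says.** Section 9.7.4.1 compares risk and reference periods within the Q/LAIV recipients; the reference is "43 to 84 days post vaccination for the risk periods of 1 to 14, 15 to 42, and 1 to 42 days". The Cox model adjusts for age, gender, health care utilization and calendar time. For respiratory outcomes, the footnote to Table 9.3-1 states that "the period at risk after vaccination for all other events of interest begins 1 day after vaccination (Day 1").

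The same section names the healthy patient effect once. If a significant increase is found, a further model with a reference period before vaccination may be built, and in it "the reference period prior to vaccination would exclude the week immediately prior to vaccination". No corresponding step is given for the days just after vaccination.

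Section 9.7.3 judges each HR against 1.00 in both directions. Besides the rule for an increase, "a statistically significantly decreased risk associated with Q/LAIV vaccination will be declared if the upper bound of the HR 95% CI is" below 1.00. Section 9.9 presents the within-cohort comparison as the control for indication bias and does not list this effect among the limitations.

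**The concern.** Dropping the week before Day 0 makes sense only if people who are acutely ill tend to put off vaccination. If they do, recipients are an unusually well group on Day 0. Respiratory visits in the next few days must then come mostly from illness that began after vaccination, whereas Days 43-84 carry the full background rate. The plan deals with one side of Day 0 and leaves the other side, its own risk window, untouched.

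The existing safeguard cannot catch this. It is triggered only by a significant increase, and the bias pushes the other way. A pre-vaccination reference would also leave the depleted risk window as it is.

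Days 1-14 is where an early live-virus effect is most plausible: the annexed package insert puts the highest proportion of subjects shedding at Days 2-3 and warns of wheezing in some recipients. At stake are a decreased risk attributed to the vaccine when there is none, and a modest early excess hidden in this comparison.

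**Working it through.** **Inputs from the protocol.** "All statistical tests will be 2-sided and performed at the significance level of 0.05" (Section 9.7.3). Section 9.5 states that "A sample size of 10,000 children will provide approximately 90% power to observe a statistically significant increase in relative risk (RR) of 1.5"; the comparison-group rate it assumes is 1%. Expected total enrollment is about 80,000.

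**The plan's own figure.** For 1.0% versus 1.5% with 10,000 per group, SE = √[(0.01×0.99 + 0.015×0.985)/10,000] = 0.00157. Then z = 0.005/0.00157 − 1.96 = 1.22, and power is 0.889. The stated 90% reproduces and is not in dispute.

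**Assumptions not in the documents.** A fraction q of acutely ill people defers vaccination (20-100%). The onset-to-visit delay is exponential with mean m (2-6 days). The hazard k days after vaccination is then background × (1 − q·e^(−k/m)).

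**No-effect HR, constant background.** HR₀ = 1 − (q/L)·Σe^(−k/m), summed over a window of L days. Depletion in Days 43-84 is negligible: e^(−43/6) is below 0.001. For Days 1-14 the sum is 1.54, 3.41 and 4.98 at m = 2, 4 and 6.

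| m (days) | q = 20% | q = 50% | q = 100% |
|---|---|---|---|
| 2 | 0.98 | 0.95 | 0.89 |
| 4 | 0.95 | 0.88 | 0.76 |
| 6 | 0.93 | 0.82 | 0.64 |

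For Days 1-42 at m = 4 the sum is 3.52, so HR₀ runs from 1 − 0.2×3.52/42 = 0.98 to 1 − 3.52/42 = 0.92.

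**No-effect HR, calendar-time Cox model.** This solves the expected partial-likelihood score, with vaccination dates spread with SD 20-30 days (assumed). With q = 0 the HR is 1.00 even with a seasonal baseline, so seasonality is handled as intended. With depletion, Days 1-14 gives about 0.66-0.98 over the whole range and about 0.77-0.96 at m = 4. Days 1-42 gives about 0.94-0.99 at m = 4. Calendar matching therefore softens the bias slightly but does not remove it.

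**Effect on the decision rule, m = 4.** P(decrease declared) = Φ(−1.96 − log HR₀/SE). With 80,000 recipients and a rate of 1 in 100 per 42 days (assumed for these outcomes), SE is about 0.10-0.13.

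- 50% deferral, HR₀ = 0.903, SE 0.13: Φ(−1.96 + 0.78) = 0.12.
- 100% deferral, HR₀ = 0.786, SE 0.10: Φ(−1.96 + 2.41) = 0.67.
- 20% deferral, HR₀ about 0.96: 0.05 (SE 0.13) to 0.06 (SE 0.10).
- A different assumed seasonal baseline gave 0.15-0.77 for 50-100% deferral.
- With 10,000 recipients the SE is √8 = 2.83 times larger. The first two cases become about 0.05 and 0.13. The 0.77 case (z = 2.70, divided by 2.83 = 0.95) becomes 0.16.

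The nominal value throughout is 0.025.

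**A real early excess.** A true HR of 1.3 reads 1.3×0.786 = 1.02 to 1.3×0.903 = 1.17. At SE 0.10, power Φ(log HR/SE − 1.96) falls from 0.75 to between 0.04 and 0.35.

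With 10,000 recipients, 100 reference events and a true HR of 1.5, there are 50 events expected in Days 1-14 without depletion. SE = √(1/100 + 1/50) = 0.173 and power is 0.65. The same calculation gives 0.26 if HR₀ is 0.85 and 0.09 if it is 0.75.

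**The case against.** The strongest reply is that the comparison with matched IIV recipients is already planned. They too are vaccinated on their own Day 0, in the same month and at the same medical center, so deferral for illness largely applies to both groups. Table 9.3-1 lists Days 1-14 as a period at risk, and Section 9.7.3 compares those periods with controls. (Section 9.7.4.2 omits Days 1-14, but names its windows only as examples.) This stands. A reader might infer that a real early excess would be cancelled for the whole study. The documents do not support that: it would be attenuated in one of three comparisons. But the IIV comparison is a separate HR with acknowledged residual confounding, and it does not stop a decrease being declared from the within-cohort HR.

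A reader might also take it as given that recipients are well on Day 0. No passage says so, there are no exclusion criteria, and the premise is inferred from the protocol's own mention of the effect. Nor is the net direction settled: respiratory events have no prior-record rule, so follow-up visits for an existing episode also count and could push the HR up. The point is therefore conditional on deferral.

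Extending it to all-cause hospitalization is not well supported, because an onset-to-visit model for acute illness does not fit that outcome.

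Finally, the study is hypothesis generating, and Section 9.7.3 warns that unadjusted intervals will exclude 1 by chance. That caveat covers chance, not systematic bias, and the further assessment it offers is for observed increases only.

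**Conclusion.** The concern holds in conditional form. If acute illness defers vaccination, as the protocol's own precaution presumes, the no-effect HR for Days 1-14 versus 43-84 is below 1 for lower respiratory events, wheezing and respiratory hospitalization. Nothing in the planned model corrects it.

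The size cannot be derived from the documents. It could be trivial (HR 0.98) or substantial (0.66), depending on the deferral fraction and the delay. The chance of a false decrease is material mainly when all 80,000 recipients are pooled and deferral is 50% or more; in a 10,000-recipient analysis it is about 5-16% at a 4-day delay. Days 1-42 is little affected, and Days 15-42 is unaffected if depletion ends by Day 14. The change is worth making, but the study as a whole is not undermined.

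**What to change.** For lower respiratory events, wheezing and respiratory hospitalization:

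1. Fit the same risk-versus-reference model in the matched IIV recipients. Report the ratio of the two within-cohort HRs (a period × vaccine term in one pooled model) as a supplementary result beside the Q/LAIV Days 1-14 HR.
2. Amend Section 9.7.3 so that no decreased risk is declared from the within-cohort Days 1-14 HR alone.
3. List this bias in Section 9.9.

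The data are already planned: "Data will be collected on subjects for 180 days following vaccination (or the index date for unvaccinated controls"). The cost is one extra model and two short text changes. The ratio has about √2 = 1.4 times the standard error of a single HR if both groups contribute similar information, and it removes only the selection that both vaccine groups share. It should therefore supplement the planned HR, not replace it.

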#### **9.7.4.2 Analyses Versus Matched Controls**

Analyses will be conducted to see if the incidence of safety outcomes is higher among Q/LAIV recipients compared to matched controls (unvaccinated or IIV) within post-vaccination “risk” periods (eg, 0 to 3 days, 1 to 42 days, and 1 to 180 days post vaccination).

This will be accomplished in the Cox models by evaluating the main effect of “treatment group.” Covariates, stratification factors, and the calendar time structure will be incorporated to control for the effects of age, gender, level of health care utilization, and seasonal difference in background event rates.

The main effect variable “treatment group” will be coded as follows:

*Treatment (for unvaccinated control analysis)*: 1 = Q/LAIV, 0 = unvaccinated

*Treatment (for IIV control analysis)*: 1 = Q/LAIV, 0 = IIV

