## 9 Research Methods

### 9.1 Study Design

Similar to previous postmarketing safety studies conducted with FluMist (Studies FM025 and MI-MA162), this study will be conducted using data collected by the Kaiser Permanente (KP) Vaccine Study Center. In this nonrandomized, observational cohort study, children and adults will be immunized with Q/LAIV as part of routine clinical practice at Northern California Kaiser Permanente (NCKP) sites. Using existing data on healthcare utilization, rates of medically attended events (MAEs) of interest will be evaluated in all eligible Q/LAIV recipients who are vaccinated in the KP Northern California Health Care Plan during the 2013-2014 influenza season. Before the study is completed enrollment must include a minimum of 10,000 children 2 through 8 years of age; based on previous utilization of FluMist at NCKP, enrollment is expected to include approximately 80,000 children and adults 2 to 49 years of age.

Incidence rates of medically attended events (MAEs) and hospitalizations during periods of risk after Q/LAIV vaccination will be compared versus incidence rates during reference periods later in the follow-up (within-cohort analysis) and versus rates in 2 nonrandomized control groups: matched unvaccinated controls and matched concurrent IIV recipient controls identified from the KP healthcare database. Trivalent inactivated vaccine (TIV) recipients will serve as controls along with quadrivalent inactivated influenza vaccine (QIIV) recipients, if a QIIV is approved and administered during the study period.

As observed in previous studies, it is anticipated that children and adults vaccinated with Q/LAIV will differ from those vaccinated with IIV or those unvaccinated in multiple underlying characteristics, such as health-seeking behavior, health status, and various demographic and socioeconomic factors. Within-cohort, risk-interval analysis control helps to control for many of these differences (Farrington et al, 1996; Yih et al, 2011; Andrews, 2002). To help reduce confounding due to differences between Q/LAIV recipients and unvaccinated and IIV controls, controls will be matched to Q/LAIV recipients as discussed below. However, even after matching for these factors, it is likely that other differences between Q/LAIV recipients and IIV control groups will remain and may generate biases in the observed rates of MAEs following vaccination.

The nonrandomized comparison groups will include:

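### The matched-control Cox models do not adjust for each subject's prior-year history of the common outcomes, so some confounding may remain in the HR used to declare significance

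*Protocol*

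**What the plan says.** - **Adjustment set.** Section 9.7.4.2 brings covariates, stratification factors and the calendar-time structure into the matched-control models "to control for the effects of age, gender, level of health care utilization, and seasonal difference in background event rates".
- **Matching.** Section 9.1 has controls frequency-"matched based on age (year) and medical center relative to concurrent reference Q/LAIV recipients". IIV controls must also be vaccinated in the same month.
- **Utilization.** Section 9.1 defines it in two levels: high is 2 or more visits in the prior 6 months, low is 1 or fewer, whatever the reason for the visit.
- **Available record.** Section 9.2.2 requires at least 12 months of plan membership before vaccination or index date.
- **Outcome-specific look-back.** The text after Table 9.3-1 counts an event only if the subject "does not have a prior record of the event in the 12 months prior to vaccination". This covers six diagnoses: Guillain-Barré syndrome, Bell's palsy, encephalitis, neuritis, vasculitis and narcolepsy/cataplexy.
- **High-risk conditions.** Sections 9.2.2 and 9.7.1 analyze Annex 3 conditions separately, and section 9.9 adds a complementary analysis that excludes those subjects.
- **Conceded bias.** Section 9.1 says that even after matching "it is likely that other differences between Q/LAIV recipients and IIV control groups will remain and may generate biases".
- **Decision rule.** Section 9.7.3 declares significance from the adjusted Cox HR.

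**The concern.** For any hospitalization, respiratory hospitalization, lower respiratory events and wheezing events, a subject's recent record of the same event is an obvious candidate confounder. It precedes exposure, it plausibly predicts the outcome, and the protocol gives reasons to expect it to differ between groups. Section 9.1 expects differences in health status and health-seeking behavior. The annexed package insert warns of a possible increase in wheezing in persons with asthma and in children under 5 with recurrent wheezing, which is a plausible reason for such subjects to receive IIV instead.

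The adjustment set has no variable aimed at this. A two-level visit count treats two routine visits and two wheezing visits alike, and an admission 7 to 12 months earlier falls outside its window. If IIV recipients carry more of this history, the HR against IIV is pulled below 1. In a safety study that can hide a real increase, or produce an apparent decrease, in outcomes that the label singles out. Against unvaccinated controls the direction is less clear.

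**Working it through.** **1. The plan's own figure.** Section 9.5 claims that the minimum pediatric sample of 10,000 "will provide approximately 90% power to observe a statistically significant increase in relative risk (RR) of 1.5"; the comparator risk it assumes is 1%. Section 9.7.3 says "All statistical tests will be 2-sided and performed at the significance level of 0.05". The control ratio is not given, so 1:1 is assumed. Comparing 1.0% with 1.5% at 10,000 per group gives power of 88.9%. The second scenario (20,000 per group, 0.5% v 0.75%) gives 88.7%. Schoenfeld's formula with 10,000 × (0.010 + 0.015) = 250 events gives 89.4%. The stated 90% reproduces, so this point does not rest on a wrong figure.

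**2. Bias from an omitted history variable.** Let pQ and pC be the proportions with prior-year history in Q/LAIV and control subjects, and R the hazard ratio for having that history. With no vaccine effect,

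null HR = [1 + pQ(R − 1)] / [1 + pC(R − 1)].

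The protocol gives none of these inputs. All values below are assumptions, before any credit for the utilization flag.

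| pQ | pC | R | Calculation | Null HR |
|---|---|---|---|---|
| 6% | 10% | 5 | 1.24/1.40 | 0.886 |
| 3% | 6% | 5 | 1.12/1.24 | 0.903 |
| 15% | 20% | 3 | 1.30/1.40 | 0.929 |
| 6% | 10% | 8 | 1.42/1.70 | 0.835 |
| 10% | 5% | 2 | 1.10/1.05 | 1.048 |
| 10% | 5% | 8 | 1.70/1.35 | 1.259 |

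The last two rows reverse the imbalance.

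**3. Does the utilization flag remove it?** Assume that 40% of both groups are high utilizers, that high utilization doubles the hazard, and that R = 5.

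- History in 2% v 4% of low and 10% v 16% of high utilizers: (0.6 × 1.08 + 0.8 × 1.40) / (0.6 × 1.16 + 0.8 × 1.64) = 1.768/2.008 = 0.880.
- History in 2% v 3% and 10% v 14%: 1.768/1.920 = 0.921.
- History balanced within strata (3% and 12% in both groups): 1.00.

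The flag therefore removes the bias only if history is balanced within its two levels. If it removed half of the first case in step 2 on the log scale, √0.886 = 0.94 would remain, and a true HR of 1.10 would read 1.10 × 0.94 = about 1.04 (1.03 to 1.04).

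**4. Consequence for decisions** (10,000 per group, 1% comparator risk, 1:1 assumed).

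- At a true RR of 1.5, a residual bias factor of 0.95, 0.90, 0.85 or 0.80 lowers power from 88.9% to 78%, 63%, 45% or 27%.
- With no true effect, a factor of 0.85 gives a significant decreased risk in 20% of studies, and in 88% at 80,000 per group.
- With no true effect, a factor of 1.15 gives a significant increased risk in 17% and 82%.

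**The case against.** The strongest reply is that the protocol already handles much of this. The utilization flag enters the same Cox model. Annex 3 includes asthma and reactive airways disease, and section 9.9 commits to an analysis without those subjects. The within-cohort comparison uses Q/LAIV recipients only, covers all four outcomes and is not exposed to baseline differences between groups. Residual bias is disclosed and the study is called hypothesis generating. Sections 9.1 and 9.9 introduce the covariates with such as, so the list is arguably open, and final covariates are often left to an analysis plan. The bias figures are all assumed.

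Much of this stands, and it rules out three stronger readings that a reader might infer.

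- *That the prior record serves only to screen rare events.* It also supplies the utilization covariate, and diagnosis codes define the high-risk groups.
- *That the rare-event look-back is confounder control applied inconsistently.* It is a case definition that keeps old disease from being counted as new. It shows that the 12-month record can be searched, nothing more.
- *That baseline differences stay in the HR in full, or must push it below 1.* Matching, utilization and the high-risk exclusion may take out part, and the documents give neither size nor direction.

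What does not stand is that these measures repair the matched-control HR itself. High-risk subjects remain in the main comparison because there are no exclusion criteria, and the analysis without them is complementary. Annex 3 has no category for prior admission, pneumonia or recurrent wheezing. The within-cohort analysis is a separate comparison. And whatever the openness of section 9.1, section 9.7.4.2 names a definite set.

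**Conclusion.** The point holds as a gap in the adjustment set, not as a demonstrated bias. The HR on which section 9.7.3 declares significance is not adjusted for prior-year history of the four common outcomes, although the required membership makes that history available and the protocol itself gives reasons for the groups to differ on it.

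How much bias would remain is unknown. The range of about 0.84 to 0.93 assumes more history among IIV recipients and no help from existing covariates. A reversed imbalance gives values above 1 (1.05 to 1.26 in the cases shown), and balance within utilization strata gives 1.00. Even a factor of 0.95 would cost about 11 points of power at RR 1.5 under the assumed 1:1 ratio (88.9% to 78%), which is enough to justify a covariate that is cheap to derive.

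**What to change.** In section 9.7.4.2, for the models of any hospitalization, respiratory hospitalization, lower respiratory MAEs and wheezing MAEs against both control groups:

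- Add the subject's history of the same outcome in the 12 months before vaccination or index date, ending 7 days before it. This keeps out the current illness and matches the week that section 9.7.4.1 already leaves out of its optional pre-vaccination reference period.
- Code it as 0, 1, or 2 or more, collapsed to yes/no where levels are sparse, for example respiratory hospitalization within age or setting subgroups.
- Report the HR with and without this covariate, so that its influence is visible.

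The cost is one derived variable from records already within the required membership year. There is a small downside: prior outcome visits partly overlap the utilization covariate, and sparse levels in small subgroups could make the Cox interval inestimable and trigger the unadjusted exact method of section 9.7.3, hence the rule for collapsing. While editing, reconcile the utilization window, which section 9.1 defines over 6 months and section 9.7.3 describes as prior year.
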